9.2.1. Treatment Assignment Procedures

This is a one-arm pilot trial, and as such all participants will receive the intervention.

9.3. Interim analyses and Stopping Rules

No interim analyses are planned. There are no stopping rules.

9.4. Outcomes

9.4.1. Primary outcome

The primary outcome is medically treated falls, defined as falls for which medical care is received. Our measure of the primary outcome will be time to first medically treated fall. The time window of observation for the primary outcome will be 6 months subsequent to the patient-facing materials being distributed to study participants. We will ascertain this outcome from health plan utilization files using International Classification of Disease-10 injury diagnosis and fall-related (V-code or W-code) external cause of injury codes.²⁰⁻²² We will describe fall events according to sex and race/ethnicity.

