6.2. Description of Evaluations

The pilot study evaluation (Aim 2) will assess 1) feasibility of reaching the target population, 2) acceptability of the intervention, and 3) success of intervention implementation.

Intervention feasibility will be measured by the ability to pull baseline data such as participant contact information, eligibility/ineligibility criteria, and demographics. If no more than 30% of intervention materials are “returned to sender,” we will deem it feasible to reach the target population.

Intervention acceptability will be measured by responses on returned questionnaires. If at least 65% of returned questionnaires indicate the intervention is acceptable and [if applicable] open-ended comments are positive >50% of the time, we will deem the intervention to be acceptable to the target population.

Intervention implementation success will be measured by documentation of a plan to taper in the “sig” field in the participant’s medical record; if at least 35% of participants have a documented taper plan, we will consider the intervention to have been successfully implemented.

Feasibility of obtaining outcomes data from the medical record will be assessed in Aim 3. Outcomes (clinical and utilization) data will be summarized and presented as percent of the study sample with the event (e.g., percent with a medically treated fall; percent with any ED visit or hospitalization, percent with a skilled nursing facility stay). Time to first medically treated fall will also be recorded.

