9.5. Data Analyses

We will summarize measures of feasibility and acceptability using binary outcomes and calculating proportions and 95% confidence intervals using simple descriptive analysis. For our primary endpoint of implementation success, following the framework proposed for pragmatic pilot trials,³⁹ if 35% have a documented taper plan, the trial will be “green” lighted to move forward to a confirmatory study; if 20%–<35% have a documented taper plan, it will be “yellow” lighted, meaning that the intervention needs to be modified if to move forward; and if <20% have a documented taper plan, it will be “red” lighted, meaning that the intervention is a “no go”. The same framework will be applied across secondary endpoints. We will examine differences by relevant sociodemographic characteristics (e.g., race, ethnicity, sex) for each outcome using the same criteria.

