10. DATA COLLECTION AND QUALITY ASSURANCE

10.1. Data Collection Sources

There will be two sources of data collection for this research project: 1) KPWA automated data sources and 2) a mailed questionnaire.

- 1) KPWA automated data sources and electronic medical records:** KPWA automated data sources will be used to complete both Aims 2 and 3. Automated data sources such as demographics, prescription medication fills, and diagnoses will be used to identify and mail to eligible participants for Aim 2. In order to ascertain the occurrence of deprescribing, we will look at the electronic medical records of participants to determine whether a plan to taper the target medication was documented. For Aim 3, we will use automated data sources to collect and summarize the following outcomes of interest: 1) medically treated falls (primary clinical outcome), 2) all-cause emergency department visits and hospitalizations, and 3) nursing home placement.

Table 1: Data from KPWA to identify potential study participants

Source (specify (i.e., from KPWA, or an existing or previous study, etc.))	List of electronic data that will be used to identify potential participants
KPWA electronic data sources	Healthcare Utilization: all outpatient visits, dates, provider id
KPWA electronic data sources	Pharmacy Dispensing Data: drug name, NDC, strength, quantity, days supply, prescriber id, and date dispensed for all medications of interest (antipsychotics, opioids, benzodiazepines, tricyclic antidepressants, Z-drugs, other sedative hypnotics, muscle relaxants, antihistamines) and medications to treat Alzheimers/dementia
KPWA electronic data sources	Diagnosis Codes: all fall and fracture related diagnoses and dates of diagnoses, all opioid use diagnoses codes and dates (exclusion criteria)
KPWA electronic data sources	Demographics: age, sex, race, and ethnicity
KPWA electronic data sources	Tumor Registry: dates of all cancer diagnosis (exclusion criteria)
KPWA electronic data sources	Procedures: all fall and fracture related procedure codes and dates of procedure
KPWA electronic data sources	Enrollment: enrollment in KPWA (start and stop dates)
KPWA electronic data sources	Provider table: provider id, specialty, provider type
KPWA electronic data sources	Referral for nursing homes and/or hospice (Exclusion Criteria)

KPWA electronic data sources	Hospice admissions database (Exclusion Criteria to confirm that these patients are not receiving hospice care)

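### Falls are defined as time to first event but summarised as a crude percent with no censoring rule, so participants who leave the health plan count as non-fallers and the 6-month risk is slightly understated

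*Combined protocol and SAP*

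**What the plan says.** Section 9.4.1 makes medically treated falls the primary outcome and states: "Our measure of the primary outcome will be time to first medically treated fall". It fixes the window: "The time window of observation for the primary outcome will be 6 months subsequent to the patient-facing materials being distributed to study participants". It also fixes the source: "We will ascertain this outcome from health plan utilization files".

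Section 6.2 gives the planned summary: "Outcomes (clinical and utilization) data will be summarized and presented as percent of the study sample with the event". It then adds: "Time to first medically treated fall will also be recorded". No estimator is attached to the recorded times.

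Section 9.5 plans on "calculating proportions and 95% confidence intervals using simple descriptive analysis", and ties this to the measures of feasibility and acceptability. It names no time-to-event method, and no confidence interval is stated for falls.

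Section 10.1, Table 1, lists "enrollment in KPWA (start and stop dates" among the data for identifying participants. Table 2, which lists the outcome data, names neither an enrolment end date nor a death date. Deaths appear as safety events in sections 7.3 and 7.3.1. No section says how disenrolment or death enters the falls analysis, or requires continuous enrolment after mailing.

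**The concern.** The measure named for the primary outcome has no stated analysis, and the summary that is stated ignores incomplete observation. A fall after someone leaves the plan would be expected not to reach the plan's utilization files. With the whole study sample as denominator, that person is scored as having had no fall, although part of the window was never observed. The error runs in one direction. The quality check in section 10.3 reviews the data that were returned, so it cannot find events that never entered the files. The same applies to emergency department and hospital use and to nursing home placement, which section 9.4.2 also takes from utilization files.

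Two things are at stake. Aim 3 asks whether pragmatic ascertainment of these outcomes is feasible. The share of people observable for the full 6 months bears directly on that question, and no section plans to report it. In addition, sections 9.1 and 14 say the pilot is to inform a full-scale trial. If its fall percent were carried into that planning, the bias would go with it and would not shrink with a larger sample.

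**Working it through.** **Figures in the plan.** The documents give no fall, death or disenrolment rate and no power for falls. The only related figure is the n=78 in section 9.2, for implementation success (20% against 35%, one-sided 5%, 90% power). It reproduces:

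- Without continuity correction, n = [1.645×√(0.20×0.80) + 1.282×√(0.35×0.65)]² / 0.15² = 71.6.
- With continuity correction, n = (71.6/4) × [1 + √(1 + 2/(71.6×0.15))]² = 78.1.

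No fall risk enters this calculation, so changing the falls estimator leaves both 78 and 120 as they are.

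**Set-up for falls (all rates assumed).** Let F, D and C be the 6-month risks of fall, death and disenrolment, each taken as if the other two did not occur. Assume constant, independent hazards, with the 6-month window as the time unit: f = −ln(1−F), d = −ln(1−D), c = −ln(1−C).

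- Crude percent (section 6.2): f/(f+d+c) × [1 − (1−F)(1−D)(1−C)]
- Actual 6-month risk (death competing, disenrolment censored): f/(f+d) × [1 − (1−F)(1−D)]
- One minus Kaplan-Meier with deaths also censored: F

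**Worked case, F=15%, D=10%, C=5%.** f = 0.1625, d = 0.1054, c = 0.0513.

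- Actual risk: 0.1625/0.2679 × (1 − 0.765) = 14.26%.
- Crude: 0.1625/0.3192 × (1 − 0.7268) = 13.91%.
- Difference: −0.34 points, or about 0.4 of a person in 120.

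**Range** (differences are taken before rounding):

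| F | D | C | Crude | Actual risk | Crude − actual | 1−KM, deaths censored |
|---|---|---|---|---|---|---|
| 5% | 0 | 2% | 4.95 | 5.00 | −0.05 | 5.00 |
| 15% | 10% | 0 | 14.26 | 14.26 | 0 | 15.00 |
| 15% | 0 | 5% | 14.63 | 15.00 | −0.37 | 15.00 |
| 15% | 10% | 5% | 13.91 | 14.26 | −0.34 | 15.00 |
| 20% | 0 | 10% | 19.02 | 20.00 | −0.98 | 20.00 |
| 30% | 15% | 10% | 26.53 | 27.82 | −1.30 | 30.00 |
| 30% | 0 | 10% | 28.56 | 30.00 | −1.44 | 30.00 |

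The bias is close to half the disenrolment proportion times the fall risk: 0.5 × 0.05 × 0.15 = 0.375 points, against 0.37 in the third row. Setting c = 0 makes the first two formulas identical, so death alone gives zero bias.

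**Against sampling error at n=120.** The half-width is 1.96×√(p(1−p)/120): 3.9 points at 5%, 6.4 at 15% and 8.2 at 30%. The largest bias in the table, 1.44 points (about 1.7 people in 120), is roughly one-sixth of the half-width at that risk.

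**The case against.** The strongest defence is that this is a one-arm pilot with no hypothesis test on falls. Aim 3 is about whether outcomes can be ascertained, and a descriptive percent is an ordinary summary for that. The protocol also does record time to first fall. The numeric boundaries in section 9.5 concern documented taper plans. The section extends the framework to secondary endpoints but gives no boundary for falls. The bias is well inside the confidence interval, and the documents nowhere say that this percent will be the event-rate input for the later trial. All of this stands and lowers the severity. It does not supply the missing estimator or censoring rule, and it does not make an unobserved person a non-faller.

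A reader might infer that deaths also push the percent down. The documents do not support that. Section 9.4.1 concerns a fall that receives medical care within 6 months, and someone who dies first without one did not have the event. A risk in the hypothetical absence of death is nowhere stated as the target. Censoring deaths in a Kaplan-Meier analysis would overstate the actual risk (15.00% against 14.26% in the second row).

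A reader might also take a loss of 10% or 20% to turn a 20% risk into 19.0% or 18.0%, a relative error of 5–10%. That holds only if all the loss is disenrolment, and the documents give no rate to support either figure.

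Nor are all the needed data already specified for the analysis: stop dates are listed for identifying participants, and deaths for safety reporting.

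**Conclusion.** The point holds and is minor. The falls measure is defined as time to event, its planned summary is a crude percent of everyone mailed, and no rule covers incomplete enrolment. Disenrolment biases that percent downward; death does not. Under the assumed ranges the understatement is about 0.05 to 1.4 points, smaller than the half-width of 3.9 to 8.2 points at n=120. The size rests on the assumed rates and on constant, independent hazards. The direction rests on falls after disenrolment not reaching the plan's files, which follows from the stated source but is not said outright. A reader should not conclude that the pilot's go/no-go decision is affected.

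**What to change.** - **Section 9.5:** estimate the 6-month cumulative incidence of first medically treated fall (Aalen-Johansen) with a 95% CI, censoring at disenrolment and treating death as a competing event. Do the same for emergency department and hospital use and for nursing home placement. Align section 6.2 with this.
- **Section 10.1, Table 2:** add enrolment end date and death date as outcome data, covering the full 6-month window.
- **Aim 3 reporting:** give the counts of deaths and disenrolments, and the percent observable for the full 6 months as a feasibility measure. These counts also help readers judge the estimator's assumption that leaving the plan is unrelated to fall risk.

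The cost is one added line in the data pull and a few lines of analysis code. The sample size is unchanged.

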9.4.2. Secondary outcomes

Secondary outcomes are 1) all-cause emergency department visits and hospitalizations, and 2) nursing home placement. Secondary outcomes will be ascertained from utilization files of the health plan.

9.5. Data Analyses

We will summarize measures of feasibility and acceptability using binary outcomes and calculating proportions and 95% confidence intervals using simple descriptive analysis. For our primary endpoint of implementation success, following the framework proposed for pragmatic pilot trials,³⁹ if 35% have a documented taper plan, the trial will be “green” lighted to move forward to a confirmatory study; if 20%–<35% have a documented taper plan, it will be “yellow” lighted, meaning that the intervention needs to be modified if to move forward; and if <20% have a documented taper plan, it will be “red” lighted, meaning that the intervention is a “no go”. The same framework will be applied across secondary endpoints. We will examine differences by relevant sociodemographic characteristics (e.g., race, ethnicity, sex) for each outcome using the same criteria.

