4.3. Study Enrollment Procedures

1. This project will request a waiver of consent to send out the educational brochure and collect data from the electronic medical record (EMR), because mailed educational material could reasonably be sent to patients from their healthcare home as part of routine care, and because decisions about any changes to medications will rest with the patient, their care partner, and their PCP. Therefore, there will not be a process for the participant to opt-out of the study. See section 11.2 for details. The project will request a waiver of documentation of consent for the questionnaire; completing and returning the questionnaire indicates permission to use responses for research.
2. Before commencing data pulls, the study team will email the Medical Chief at each intervention clinic to alert them that this pilot intervention is going to commence. Because the intervention and implementation are very comparable to that of STOP-FALLS, which these clinicians are already familiar with due to having been based in intervention clinics for the STOP-FALLS trial, a more in-depth clinic presentation to providers is not deemed necessary.
3. Using KPWA automated data under a waiver of HIPAA authorization, the study programmer will identify all potential participants who meet inclusion criteria. The programmer will oversample participants who are of Hispanic ethnicity and whose race is not white. Of this potential participant pool we will identify a total study sample of 120 participants to whom we will mail the study materials.

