9.2. Sample Size and Randomization

For Aims 2 and 3, our sample size calculations are based on the framework of “green”, “yellow” and “red” lighting for pilot feasibility trials.³⁹ Based on our primary endpoint, which is implementation success,¹⁷ assuming the upper boundary of the “red” zone is 20% and the lower boundary of the “green” zone is 35%, the sample size required for analysis given 90% power and one-sided 5% alpha is $n=78$ (intervention arm only). Specifically, if the true rate is in the “green” zone with a sample size of 78, we have 90% power for the study to not be defined as “red” lighted. We will increase the sample size to 120 to be able to have 90% power across all secondary endpoints as well.

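### Under section 9.5, a difference in colour between sociodemographic subgroups cannot be told from chance

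*Combined protocol and SAP*

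**What the plan says.** Section 9.5 sets the rule for the primary endpoint, implementation success, on the observed percentage with a documented taper plan. At 35% the trial is green. In the middle band, "if 20%–<35% have a documented taper plan, it will be “yellow” lighted, meaning that the intervention needs to be modified if to move forward". Below 20% it is red, which the plan equates with not going ahead. The same framework is extended to the secondary endpoints, and the section ends: "We will examine differences by relevant sociodemographic characteristics (e.g., race, ethnicity, sex) for each outcome using the same criteria".

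Section 9.2 sizes these cut-offs for the whole sample: 20% against 35%, one-sided 5% alpha and 90% power give n=78. The stated reason for going beyond 78 is the other endpoints, not subgroups: "We will increase the sample size to 120 to be able to have 90% power across all secondary endpoints as well".

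Section 4.3 adds: "The programmer will oversample participants who are of Hispanic ethnicity and whose race is not white". No target number or fraction is given. For subgroups the plan gives no expected size, no confidence interval for a difference, no multiplicity rule and no exploratory label.

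**The concern.** The only criteria defined just before the subgroup sentence are the colour cut-offs. The natural reading is therefore that each racial, ethnic or sex group is given a colour and the colours are compared.

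A colour is a cut of an observed percentage and carries no uncertainty. In a group of 20, one participant is 5 percentage points, while the yellow band is only 15 points wide. Two groups with the same true rate can easily land on different sides of a boundary.

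The précis says the project should include people from diverse backgrounds, and section 9.1 says the pilot is to inform a full-scale trial. A colour that one group received by chance could be taken as a finding about that group when the larger trial is designed.

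**Working it through.** **1. The plan's own figure.** Inputs from section 9.2: p0 = 0.20, p1 = 0.35, one-sided alpha 5% (z = 1.645), power 90% (z = 1.282).

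n = [(1.645·√(0.20·0.80) + 1.282·√(0.35·0.65)) / 0.15]² = 71.6.

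With the continuity correction, (n/4)·[1 + √(1 + 2/(n·0.15))]² = 78.1. The stated 78 is reproduced, as a whole-sample figure.

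**2. Colour probabilities for one group.** With X ~ Binomial(n, p): green if X/n ≥ 35%, yellow if 20% ≤ X/n < 35%, red if X/n < 20%. At n=60 this means red up to 11, yellow 12–20, green from 21. At n=20 it means red up to 3, yellow 4–6, green from 7.

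At a true rate of 27.5%, the middle of yellow:

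| n | red | yellow | green | wrong colour |
|---|---|---|---|---|
| 120 | 2.3% | 93.3% | 4.4% | 6.7% |
| 60 | 7.0% | 80.5% | 12.5% | 19.5% |
| 30 | 12.8% | 69.5% | 17.7% | 30.5% |
| 20 | 15.8% | 54.3% | 29.9% | 46% |

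A group of 20 with 7 taper plans (35%, green) has an exact 95% CI of 15–59%, which spans all three colours.

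**3. Two subgroups with the same true rate.** P(different colours) = 1 − (R₁R₂ + Y₁Y₂ + G₁G₂).

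- 60/60 at 27.5%: 1 − (0.070² + 0.805² + 0.125²) = 1 − 0.669 = 33.1%.
- 100/20 at 20%: 1 − (0.460·0.411 + 0.540·0.502 + 0.0003·0.087) = 1 − 0.460 = 54.0%.

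The splits of 120 are assumptions. The documents give no expected taper rate, so the table spans a wide range of true rates:

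| True rate in both | 60/60 | 72/48 | 80/40 | 90/30 | 100/20 |
|---|---|---|---|---|---|
| 10% | 2.9% | 2.3% | 4.7% | 7.6% | 13.4% |
| 15% | 29.6% | 24.8% | 31.5% | 34.1% | 38.6% |
| 20% | 50.0% | 50.5% | 50.6% | 50.8% | 54.0% |
| 27.5% | 33.1% | 34.7% | 36.5% | 35.8% | 48.4% |
| 35% | 49.9% | 50.9% | 50.1% | 51.2% | 51.4% |
| 40% | 29.3% | 33.7% | 29.9% | 36.2% | 31.7% |
| 45% | 8.5% | 11.1% | 9.8% | 15.5% | 14.2% |
| 50% | 1.3% | 2.1% | 2.2% | 5.1% | 5.8% |

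Red against green (R₁G₂ + G₁R₂) is at most 4.0% in any cell (100/20 at 20%). Nearly all chance mismatches are between adjacent colours.

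**4. Four subgroups with the same true rate.** For assumed sizes 40/30/30/20, all four share one colour in 19% of trials at a true 27.5% and in 12% at 35%. The figure rises to 71%, 60% and 84% at 10%, 45% and 50%.

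**5. A real difference of 35% against 20%.** Over the same splits, with either group the higher, colours differ in 71–78% of trials. For groups with a common true rate of 20–40%, a mismatch is therefore only about 1.3 times (72.1/54.0, at 100/20) to 2.6 times (75.1/29.3, at 60/60) as likely under this real difference as under none. Red against green is more informative, but even with this real difference it appears in only 21–28% of trials.

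**The case against.** **The range of true rates matters.** Mismatch is most frequent between and near the cut-offs. At true rates of 10%, 45% or 50% it is 1–16%. This stands, and the full range is shown for that reason. The problem is still material from about 15% to 40%, the region in which the cut-offs were set to discriminate.

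**Subgroup sizes are assumed.** This also stands. Oversampling would enlarge the minority groups and so reduce the problem. Yet an equal split of 60/60, the least affected of the five splits at mid-yellow, still gives 33% mismatch there.

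**A reader might infer that observed colour differences will be mostly chance.** The documents do not support that, because it depends on how large real differences are. One simulation assumed a mean rate uniform on 15–45% and two subgroups. The share of mismatches arising between groups in the same true colour zone was 65–69% if real differences have an SD of 5 points, 38–44% at 10 points and 24–30% at 15 points. The plan gives no basis for choosing among these.

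**A reader might also infer that one ethnic group would be formally stopped.** The plan does not say so. In section 9.5 the light belongs to the trial, and the subgroup sentence speaks only of examining differences. A false red is also uncommon for a group whose true rate is 35%: 4.4% at n=20, 2.3% at n=30 and 0.4% at n=60.

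**Intervals are partly planned.** Section 9.5 provides 95% CIs for feasibility and acceptability measures. It does not expressly extend them to subgroup taper proportions or to differences between subgroups, so they do not settle the matter. One could also read the closing words of the subgroup sentence as meaning only the same descriptive method. If that was intended, the sentence should say so.

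**Conclusion.** The point holds in a limited form. If the colour criteria are applied within subgroups, a difference in colour between them cannot be told from chance when true taper rates are roughly 15–40%. Equal-rate pairs then differ in about 25–54% of trials, against 71–78% under a real 15-point difference.

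This rests on assumed subgroup sizes, independent binomial counts, and the natural reading of the subgroup sentence. The calculation covers documented taper plans, for which section 9.5 states both cut-offs.

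The whole-sample progression result is unaffected. What is at risk is the reading of subgroup results when the full-scale trial is designed. This is a cheap improvement rather than a flaw in the main analysis.

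**What to change.** In section 9.5, delete the last four words of the subgroup sentence and add, in substance: *Subgroup results are exploratory. For each subgroup we will report n, the proportion and its 95% CI, and the difference between subgroups with its 95% CI. The colour criteria apply to the whole sample only.*

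The cost is about one sentence and no new data. Subgroup statements become less definite, as the sample warrants. At a common rate of 27.5%, the approximate 95% CI for a difference is ±1.96·√(0.275·0.725·(1/60 + 1/60)) = ±16 points for 60/60, and ±1.96·√(0.275·0.725·(1/100 + 1/20)) = ±21 points for 100/20. A two-sided 5% comparison of 35% with 20% would need 138 per group for 80% power, more than the whole planned sample of 120, so a descriptive report is what the data can support.
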